### **Secondary endpoints:**

Kidney biopsy will be performed per SOC at month 3 and 12 post-transplant. Biopsies will be evaluated and compared between two groups for CNI-related toxicities. Correlations

*Northwestern University Feinberg School of Medicine:* Extended-Release Tacrolimus Vs. Twice-Daily Tacrolimus

between kidney injury markers and biopsy data at 3 and 12 months post-transplant will be performed (details are below).

Antibody responses and correlation with CNI exposure by SOC donor specific antibody (DSA) assessment at months 3 and 12 post-transplant (performed at the Clinical Immunology Laboratory of the CTC).

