## **DATA AND SPECIMEN MANAGEMENT:**

### **Statistical analysis:**

The primary endpoints of the study are graft function and subpopulations of T cells, including regulatory T cells and B cell subpopulations as well as immune functions at 3 and 12 months post kidney transplant.

The secondary endpoints of the study include 1) incidence of acute rejection, graft loss, and death at 3 and 12 months post kidney transplant; 2) allograft immunohistopathology profiles at 3 and 12 months post kidney transplant.

We will run univariate and bivariate analyses for all variables prior to our main analyses. We will evaluate continuous variables using t-tests or F-tests and categorical variables using  $\chi^2$ . We will examine data distributions and test all variables for linear relationships or non-linear relationships.

Descriptive statistics (means, standard deviation, frequency) and correlations (both Pearson and Spearman) among variables will be calculated for preliminary data assessment.

Necessary transformation and imputations will be carried out based on the raw data distribution.

As missing data are inevitable in a longitudinal study, we will determine whether missing data are MCAR (data are missing completely at random), MAR (data are missing at random), or NMAR (not missing at random). If missing data are MCAR or MAR, it is likely that the standard multivariate computations using PROC MI (multiple imputations) will not result in biased standard error estimates. However, if missing data are NMAR, we will use the "pattern mixture" approach to compute a weighted average of the parameters that are associated with the missing data to estimate what the data would have been.

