For the primary objective, we hypothesize that subjects receiving LCP-Tacrolimus/Envarsus® XR will exhibit significantly greater graft function and lower frequency / abundance of AlloSeq pre-identified donor-reactive T cell clones in the graft, peripheral blood and /or urine at 3 and 12 month post-transplant as compared to the standard of care tacrolimus group. A variety of covariance structures (first order regressive, compound symmetry, Toeplitz, variance components, unstructured) will be carefully examined and compared using the best fitting statistics, such as Akaike's Information (AIC) and Bayesian Information Criteria (BIC). These statistics are likelihood functions and can be compared across models. If, in spite of randomization, distributions of subjects' baseline characteristics are found to be different between the two experimental groups, these variables will be entered as covariates in the statistical analysis.

For the secondary endpoints, we will use logistic regression, Kaplan-Meier method, and Cox proportional hazards models to analyze time-to-event outcomes (acute rejection, graft failure, and death). For allograft immunohistopathology outcomes, we will first develop a comprehensive immune profile of each participant by longitudinal analysis of frequency of T and B cell subsets and function. We will examine how these correlate with immunohistopathology and alloantibody production using Pearson or Spearman correlations. We will compare correlation coefficients between the two experimental groups using Z -tests to determine the distinct effects of each treatment arm. We will also compare the trajectory changes in cell populations and antibody production over 3 and 12 months using both repeated measures ANOVA and random mixed effect models. All tests will be

*Northwestern University Feinberg School of Medicine:* Extended-Release Tacrolimus Vs. Twice-Daily Tacrolimus

two-sided, and an error rate of  $\alpha <0.05$  will be considered statistically significant. All data analyses will be performed using SAS 9.2 statistical software (SAS Inc., Cary, NC).

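### The promised between-arm biopsy comparison has no specified main analysis; the Z-test on correlations named for histology answers a different question

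*Combined protocol and SAP*

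**What the plan says.** Histology appears twice as a secondary endpoint in the combined protocol and SAP. Under Study Endpoints, Secondary endpoints: "Biopsies will be evaluated and compared between two groups for CNI-related toxicities". Under Statistical analysis, the second listed secondary endpoint is "allograft immunohistopathology profiles at 3 and 12 months post kidney transplant". Neither place names a score or a test.

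The analysis text for histology is in the secondary-endpoints paragraph of Statistical analysis and has three steps:

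- "For allograft immunohistopathology outcomes, we will first develop a comprehensive immune profile of each participant";
- "We will examine how these correlate with immunohistopathology and alloantibody production using Pearson or Spearman correlations";
- "compare correlation coefficients between the two experimental groups using Z -tests to determine the distinct effects of each treatment arm".

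The other main analyses in that paragraph concern different outcomes. Logistic regression, Kaplan-Meier and Cox models are for rejection, graft failure and death. Repeated-measures ANOVA and mixed models are to "compare the trajectory changes in cell populations and antibody production over 3 and 12 months", and histology is not in that list.

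Earlier in the same section the plan says "We will run univariate and bivariate analyses for all variables prior to our main analyses". The next sentence reads "We will evaluate continuous variables using t-tests or F-tests and categorical variables using" chi-square. It does not say that treatment arm is the grouping factor.

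**The concern.** The endpoint asks whether one regimen leaves more toxicity or injury in the graft than the other. The one between-arm method written for histology compares two correlation coefficients, and the plan gives it the job of showing what each arm does. A difference in correlations is a difference in association (effect modification). It says nothing about which arm has the worse biopsies.

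Two errors of interpretation become possible. A non-significant Z-test could be taken as evidence of similar histology when the arms differ. A significant one could be taken as a treatment effect when histology is the same in both arms and only its relation to the immune markers differs.

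**Working it through.** The plan states no effect size, power or sample size for histology, so there is no figure of its own to reproduce.

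**Inputs from the documents.** 25 per arm (Number of Participants); two-sided alpha of 0.05 and 10% attrition at 12 months (Sample size and power). 25 × 0.9 = 22.5, taken as 22 evaluable per arm.

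**Inputs assumed.** The size of the histology shift, the marker-histology correlations, and the cut-points of a 4-level grade. A range is shown for the shift and the correlations.

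**Step 1: algebra.** Let X be an immune marker and Y a histology score within one arm. If every Y in that arm moves by a constant c, then cov(X, Y + c) = cov(X, Y) and SD(Y + c) = SD(Y), so Pearson's r is unchanged. Ranks within the arm are also unchanged, so Spearman's coefficient is too. The Z statistic is

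Z = [atanh(r1) − atanh(r2)] / √(2/(n − 3)),

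and it does not depend on c. This holds at any n.

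**Step 2: a shift in histology with equal correlations.** For the continuous score: 40,000 simulated trials per setting, correlations of 0, 0.3 and 0.6 (the same in both arms), 25 or 22 per arm. For the 4-level grade: 20,000 trials, correlation 0.3, 22 per arm, Z-test on Spearman coefficients.

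| Shift between arms | Score | Z-test on correlations rejects | Direct test rejects |
|---|---|---|---|
| 0.5 SD | continuous | about 5% | 37% (n = 22) to 41% (n = 25), t-test |
| 1 SD | continuous | about 5% | 90% (n = 22) to 93% (n = 25), t-test |
| 0.5 SD (latent) | 4-level grade | 4.7% | about 32%, Mann-Whitney |
| 1 SD (latent) | 4-level grade | 4.7% | about 85%, Mann-Whitney |

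The Z-test's 5% is its type I error. A latent shift on a graded scale is not exactly a constant shift in the observed grades, so the algebra holds only approximately there. The simulated rate is still at the nominal level.

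**Step 3: identical histology, different correlations.** With correlations of 0 and 0.6, atanh(0.6) = 0.693.

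- n = 25: 0.693 / √(2/22) = 0.693 / 0.302 = 2.30. Simulated rejection rate 65%.
- n = 22: 0.693 / √(2/19) = 0.693 / 0.324 = 2.14. Simulated rejection rate 59%.

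The t-test on the same data rejects about 5%, as it should.

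**Step 4: power of the Z-test for its own question.** The difference on the atanh scale detectable with 80% power is (1.96 + 0.8416) × √(2/(n − 3)).

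- n = 25: 2.8016 × 0.302 = 0.845; tanh(0.845) = 0.69.
- n = 22: 2.8016 × 0.324 = 0.909; tanh(0.909) = 0.72.

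The correlation would thus have to be 0 in one arm and about 0.7 in the other. For 0.2 against 0.5, power is about 0.21 (n = 25) or 0.19 (n = 22).

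**The case against.** A reader might infer from the above that the histology question goes untested and that a real benefit or harm on biopsy would be missed. The documents do not support that. The secondary endpoints commit to a between-group biopsy comparison, and the t, F and chi-square tests are introduced in a paragraph that covers all variables. In a two-arm randomised trial, arm is the natural grouping. It can also be argued that the phrase placing work before the main analyses belongs to the univariate and bivariate sentence alone, and that the explicit label of preliminary assessment is attached only to the descriptive statistics and correlations that follow. Those tests could therefore supply the comparison, and nothing says that the Z-test replaces it.

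That much stands. The generic sentences still do not specify a comparison: they name no grouping factor, histology score, time point or effect estimate. Nor do they alter the later sentence that gives the Z-test the task of showing treatment effects.

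Whether an immune-histology association differs by arm is a legitimate question. The Z-test may stay, provided that it is labelled as that.

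The Sample size and power section calls the study a pilot and disclaims power for secondary outcomes. This limits the stakes and excuses imprecision. It does not cover a test that fails to respond to the effect of interest at any sample size.

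Finally, the 90–93% depends on a 1 SD shift. At 0.5 SD a direct test has only 37–41% power, so a direct comparison would not be well powered for moderate differences either.

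**Conclusion.** The point holds in this form: the plan intends a between-arm biopsy comparison but specifies no main analysis for it, and the between-arm method that it does name for histology answers a different question. That the Z-test is blind to a constant shift is algebra and needs no assumption. The rejection rates are illustrations that rest on assumed shifts, correlations and cut-points. How the result would eventually be reported is not known; the risk lies in the stated purpose of the Z-test. The change is worth making, with modest stakes: no primary conclusion depends on it.

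**What to change.** In the secondary-endpoints paragraph of Statistical analysis:

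1. Name the histology score or scores for CNI toxicity and injury, so that the comparison does not run over an open-ended set of outcomes.
2. Compare the arms directly on each named score at months 3 and 12: a rank-sum test or proportional-odds model for grades, Fisher's exact or chi-square test for presence or absence. Report the between-arm difference with a 95% CI.
3. Keep the Z-test on correlations only as an exploratory test of whether the immune-histology association differs by arm, and delete the clause that says it determines the effects of each treatment arm.

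The cost is a few sentences of text and a little more analysis. No new data are needed, because biopsies are already planned at both time points.

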## **STUDY ENDPOINTS:**

### **Primary endpoints:**

One of the 2 primary end points Kidney transplant function assessed as kidney injury markers in urine samples collected at 12-hour and 24-hour trough levels and 2-hour peak levels at 2nd week, 3rd month, 12th month post transplantation, and at any for-cause biopsy event. The injury markers will be assessed using Myriad-RBM KidneyMAP panel <https://myriadrbm.com/products-services/humanmap-services/kidneymap/>.

The other primary end point is immune activation assessed through serial flow cytometric immunophenotyping for immune cells including T and B cell subpopulations as well as donor-reactive TCR repertoire analysis in biopsy, blood and urine.

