**Blood Immunophenotyping.**

The approach will be to conduct a multi-parameter flow cytometric immunophenotyping of peripheral blood before and at 3 and 12 months post-transplant to analyze cellular changes.

Methods (14-16): Our well-established 5-color flow cytometric analyses is performed using whole blood to delineate the cellular makeup in terms of both percentages and absolute numbers (**Table 1**). RBCs are lysed before flow acquisition. The analysis is for defining the T cell subsets, monocytes and natural killer cells (Tube 2), the B cells

including naïve, transitional, memory and effector-memory subsets (Tube 3) and the dendritic cells including immature, monocyteoid and plasmacytoid fractions (Tube 4).

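### Cell subpopulations are a primary endpoint, yet their trajectories are to be compared by two unranked methods, with no stated contrast and no prespecified adjustment for the pre-transplant value

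*Combined protocol and SAP*

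**What the plan says.** **Status of the endpoint.** The Primary endpoints section lists "immune activation assessed through serial flow cytometric immunophenotyping for immune cells including T and B cell subpopulations". The Statistical analysis section agrees, counting among the primary endpoints "subpopulations of T cells, including regulatory T cells and B cell subpopulations as well as immune functions at 3 and 12 months post kidney transplant". Its list of secondary endpoints (rejection, graft loss, death, immunohistopathology) does not include cell populations.

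**Analysis.** The only sentence that compares cell-population trajectories between arms plans to examine "trajectory changes in cell populations and antibody production over 3 and 12 months using both repeated measures ANOVA and random mixed effect models". It names no lead method, model term, contrast or visit, and no rule for disagreement. It stands in the paragraph on secondary endpoints.

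**Covariance.** The preceding paragraph, on the primary objective, says: "A variety of covariance structures (first order regressive, compound symmetry, Toeplitz, variance components, unstructured) will be carefully examined". The choice is made by AIC and BIC. That paragraph names no model.

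**Baseline.** The Blood Immunophenotyping section plans "multi-parameter flow cytometric immunophenotyping of peripheral blood before and at 3 and 12 months post-transplant", so each subset has a pre-transplant value. Baseline characteristics enter the analysis only if the arms turn out to differ, in which case "these variables will be entered as covariates in the statistical analysis". The outcome's own baseline is not named.

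**Error rate.** All tests are two-sided at 0.05, with no multiplicity rule.

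**The concern.** Two analyses of one primary endpoint, neither ranked, give two routes to a significant result at 0.05.

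There is also an efficiency question. A group-by-time test with the pre-transplant sample as one of the visits compares changes from baseline. When the correlation with baseline is moderate, a change score is noisier than a comparison adjusted for baseline. With 25 patients per arm that loss can matter, and the data needed to avoid it are already collected. Making adjustment depend on observed imbalance leaves the choice open until the data have been seen.

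**Working it through.** **Inputs from the documents.** 25 per arm; 10% attrition at 12 months; two-sided 0.05; flow cytometry before transplant and at months 3 and 12. **Assumed, because the documents give none:** between-visit correlation r, visit variances, 5% missing at month 3, an effect of 0.8 SD equal at months 3 and 12, and group-by-time over three visits as the ANOVA test.

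**1. The plan's own power figures.** Sample size and power gives 0.99 for an effect of 2.0 on immune activation, defined there as clonal repertoire change. A two-sample t-test with 25 per arm gives above 0.999, which is consistent. The 0.82 for an effect of 1.0 does not reproduce (0.934 with 25 per arm, 0.906 with 25 × 0.9 = 22.5), but it concerns graft function and is a separate matter. No effect size is stated for flow-cytometry subsets.

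**2. Type I error if either method may count.** Two independent tests would give 1 − 0.95² = 9.75%. These two are highly correlated; with complete data, repeated-measures ANOVA is the compound-symmetry mixed model. Simulated results with no treatment effect:

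| True covariance | Complete data, 22–25 per arm (mixed model with AIC-chosen structure) | 25 per arm, 10% missing at month 12 (ANOVA on completers, unstructured model on all data) |
|---|---|---|
| Compound symmetry, r = 0.5 | 5.3% | 6.9% |
| First-order autoregressive, 0.6 | 6.6–7.0% | 8.0% |
| Unequal variances | 7.8–8.2% | 8.7% |

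Monte Carlo standard error is 0.2–0.4 points. With a Greenhouse–Geisser correction, which the plan does not mention, the complete-data range is 5.2–7.5%.

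**3. Power at 0.8 SD, equal variances.** Write m for patients per arm.

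- *Group-by-time.* Completers: m = 25 × 0.90 × 0.95 = 21.4. Arm differences at the three visits are 0, 0.8, 0.8, with mean 0.533 and squared deviations summing to 0.284 + 0.071 + 0.071 = 0.427. The noncentrality is (m/2) × 0.427/(1 − r) = 4.56/(1 − r), that is 6.5, 9.1 and 15.2 at r = 0.3, 0.5 and 0.7. An F test on 2 and 4(m − 1) degrees of freedom then has power of about 60%, 76% and 94%.
- *Month-12 value adjusted for baseline.* m = 22.5. The noncentrality is 0.8/√(1 − r²) × √(22.5/2), that is 2.81, 3.10 and 3.76. Power by formula is about 78%, 86% and 96%. Simulation, which includes the small cost of chance baseline imbalance, gives 77%, 85% and 95%.

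**4. Is the gap only degrees of freedom or dropped patients?** No. With 22 complete patients per arm and a one-degree-of-freedom test at month 12 in both cases, simulated power for change from baseline against baseline-adjusted is 59% v 77%, 75% v 84% and 93% v 96% at r = 0.3, 0.5 and 0.7. The variance ratio is 2(1 − r)/(1 − r²) = 2/(1 + r): 1.54, 1.33 and 1.18.

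**5. Sensitivity.** If the pre-transplant SD is twice the later SD, group-by-time power runs from about 31% at r = 0.3 to a little under 50% at r = 0.7, against about 78% to 95% with adjustment. Unequal variance is plausible because alemtuzumab is given between the first and second samples, but no document gives a value. At an effect of 2.0 with equal variances both tests have power of essentially 100%. If only months 3 and 12 are analysed, group-by-time has about 5% power against an effect equal at both visits.

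**The case against.** The strongest reply is that most of the harm is inferred.

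- **The contrast is not stated.** This stands. Every ANOVA power figure above is conditional on group-by-time with baseline as a visit. The silence is itself the defect, since other readings of the same sentence give very different power.
- **The inflation is small.** This stands. A reader might infer that two tests double the error rate, or might pair ANOVA with a baseline-adjusted month-12 test and obtain roughly 8–11%. The documents do not support either. The second pair uses an analysis that the plan does not propose, and part of its upper end is ANOVA's own error when variances differ.
- **Patients need not be lost.** The plan provides for multiple imputation and, for data not missing at random, pattern mixture. It is therefore not certain that ANOVA would drop patients with a missing visit. Step 4 shows that the power gap does not depend on this.
- **The only immune effect size in the plan is 2.0**, where the gap vanishes with equal variances. True, but that figure is for clonal repertoire, not cell subsets.
- **The covariance search and the trajectory sentence are in different paragraphs.** Linking them is a reading. A reader might go on to infer that AIC/BIC selection should be removed from the whole plan. That would also reach graft function, for which the Kidney transplant function section lists no pre-transplant urine, so the model proposed here does not carry over.
- **This is a pilot.** The plan uses that status to set aside power for secondary outcomes, not primary ones.

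**Conclusion.** The concern holds in limited form. It is established from the text that cell subpopulations are primary, that two methods are planned with neither ranked, that no contrast or visit is named, and that the pre-transplant value is collected without being a prespecified covariate.

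The false-positive cost is modest: about 5–9% against a nominal 5%, depending on covariance and missing data. The power cost is conditional. If the deciding test is group-by-time over three visits and the effect is 0.8 SD, it is about 17 points at r = 0.3 (77 − 60), 9 at r = 0.5 (85 − 76) and 1 at r = 0.7 (95 − 94). It is larger if pre-transplant variance is higher.

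A reader might take the sentence's position among the secondary endpoints to mean that cell populations are secondary. Both endpoint statements contradict that.

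**What to change.** In the Statistical analysis section, for the flow-cytometry cell subsets only:

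- Name one deciding analysis: a mixed model of the month-3 and month-12 values with arm, visit, arm-by-visit and the pre-transplant value of the same subset as a prespecified covariate, unstructured covariance and Kenward–Roger degrees of freedom.
- State the between-arm contrast and the visit at which it is tested.
- Keep repeated-measures ANOVA as a labelled sensitivity analysis.
- Allow a simpler covariance only as a stated fallback for non-convergence.
- Leave AIC/BIC covariance selection for graft function outside this change.

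The cost is wording, plus a small statistical price. Unstructured covariance for two visits has 3 parameters, against 2 for compound symmetry or 1 for independence with equal variance, so one or two extra; the covariate takes one degree of freedom. No new samples are needed. The change does not settle which of the many subsets is primary; that needs its own decision.

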**Sample size and power:**

This proposal bases its sample size calculations on published data demonstrating increased peaks and troughs with conventional tacrolimus and absence of such peaks and troughs with LCP-Tacro/Envarsus® XR (1) and correlation with high doses and nephrotoxicity with conventional tacrolimus (4). Using a two-tailed  $\alpha$  of 0.05, the anticipated effect sizes corresponding to each specific aim between the two treatment arms were calculated using a minimum of 80% statistical power and assumed 10% attrition at 12 months.

For the sample size of  $n= 25$  in each group, the proposed study will have a power of 0.82 and 0.99 to detect effect size of 1.0 and 2.0 for graft function and immune activation (in terms of T cell clonal repertoire change), respectively, between the two treatment arms. Because this is a pilot study, we do not consider the statistical power of secondary outcomes; It is anticipated that a much larger sample size will be needed in order to achieve statistical power for the secondary endpoints in this proposed study.

